5.1.4 Multiple Comparison and Multiplicity

No adjustment for multiplicity will be applied to any endpoints, thus any inferential statistics will be nominal.

6 POPULATION SUMMARIES

Unless otherwise stated, listings corresponding to all summaries in this section will be provided for all randomized subjects (ITT population).

6.1 Subject Disposition

The number of subjects included in each of the analysis populations defined in this SAP and the reasons for exclusion will be summarized by treatment group. A listing will be provided to indicate each subject's inclusion/exclusion from the populations, and the reason for exclusion from a population will be presented.

A list of randomized subjects who did not meet all inclusion/exclusion criteria, and which criteria were not met will be presented.

The number and percentage of subjects completing the study (defined as completing the EOT, PTE and FFU visits, as reported on CRF), as well as the completion status of EOT, PTE, and FFU visits will be presented. Reasons for not completing the study and for missing visits, as recorded on the eCRF, will be summarized (number and percentage) by treatment group for ITT, CE and PTE populations.

The number and percentage of subjects completing and prematurely discontinuing test article and the reasons for discontinuation will be presented by treatment group. A listing of all subjects who prematurely discontinued from test article or who did not complete the study will be presented, along with the primary reason for discontinuation of test article or not completing the study for ITT, micro-ITT, CE-PTE, and ME-PTE.

The number of screen failures and reason for screen failure will be presented overall. For randomized subjects, a listing will be provided that indicates the date and time of randomization, randomization number, randomized treatment assignment, drug unit identifications, and corresponding drug codes.

6.2 Demographic and Baseline Characteristics

Demographic characteristics will be summarized for ITT, micro-ITT, CE-PTE, and ME-PTE populations. The summary table will include age, race, and ethnicity, along with baseline characteristics for height, weight, body mass index (BMI), number of prior urinary tract infections (UTIs) (lifetime), and renal function. Age will be summarized as a continuous variable and as categorical, based on the following groups: 18 to 45 years, >45 to 65 years, >65 years.

Renal function will be categorized as normal (creatinine clearance [CrCl] > 89 mL/min), mild renal impairment (CrCl > 60 to 89 mL/min), moderate renal impairment (CrCl 30 to 60 mL/min) and severe renal impairment (CrCl < 30 mL/min). Creatinine clearance will be calculated from the local laboratory data and will be determined from the Cockcroft-Gault equation, for female subjects:

$$CrCl = \frac{(140 - \text{age [yrs]}) * \text{weight [kg]} * (0.85)}{\text{Cr [mg/dL]} * 72}$$

Gender will not be included in the summary, as all subjects enrolled in this study will be female, per inclusion criteria.

General medical history and will be coded using Medical Dictionary for Regulatory Activities (MedDRA) and summarized by system organ class (SOC) and preferred term (PT).

Results of the UTI Symptoms Assessment (UTISA) questionnaire will be as the number and percentage of subjects responding to each item, including individual severity scores, individual bothersome scores, and overall severity (ITT, micro-ITT, CE populations).

6.3 Baseline Microbiology

The microbiological assessment of the urine culture by the local laboratory will be summarized by treatment group for the ITT, micro-ITT, micro-m1ITT, and micro-m2ITT populations and will include as follows:

- The number of subjects with local urine culture performed
- The number of subjects with a clean catch sample
- The number of subjects with urine culture growth
- The number of isolates per subject where CFU count $\geq 10^5$ CFU/mL.
- Each isolate identified will also be reported and will include the CFU counts as recorded on the CRF ($< 10^3$ CFU/mL, $10^3 \leq$ and $< 10^4$ CFU/mL, $10^4 \leq$ and $< 10^5$ CFU/mL, and $\geq 10^5$ CFU/mL).

Test article received disk diffusion (mm) to baseline pathogen will be provided for micro-ITT population.

All of the below reports will be provided for micro-ITT and ME populations.

- The number and percentage of subjects with a positive urine culture by pathogenic organism will be provided.
- The number and percentage of subjects with a Gram-positive organism (aerobes and anaerobes) and with a Gram-negative organism (aerobes and anaerobes) will be presented by genus and species.

The number and percentage for minimum inhibitory concentration (MIC) data will be provided as:

- The MIC distribution to omadacycline and nitrofurantoin, across treatment groups
- The MIC distribution to the test article received, by treatment group

MIC summary statistics (ie, range, MIC₅₀, and MIC₉₀) to the test article received. The MIC range will be provided for all baseline pathogens. The MIC₅₀ and MIC₉₀ will be provided only for those pathogens isolated at least 10 times in a treatment group. MIC₅₀ and MIC₉₀ values are defined as the lowest concentration of the antibiotic at which 50% and 90% of the isolates were inhibited.

MIC summary statistics (ie, range, MIC₅₀, and MIC₉₀) to the test article received for each pathogen at baseline.

A listing will be provided that includes for each subject all baseline and post-baseline isolates identified by Genus and species from the local and central urine culture including the CFU count and whether or not the isolate is a pathogen.

6.4 Medical and UTI History

Significant medical history (at any time) and any medical history within the past 6 months including ongoing medical conditions at the time of signing of the ICF will be recorded.

In addition, subject history of prior UTI infection will be captured. Where possible, diagnoses are to be recorded. Of note, any event or change in the subject's condition or health status occurring after signing the ICF will be reported as an AE. All medical history will be coded using the Medical Dictionary for Regulatory Activities (MedDRA).

The incidence of medical history abnormalities will be summarized using descriptive statistics by system organ class (SOC) and preferred term. Patients are counted only once in each preferred term and SOC category. Summaries will be presented by treatment group and for all patients.

6.5 Prior and Concomitant Medications

Treatments that have been administered within the 7 days prior to the date of informed consent, or during the Screening phase, will be recorded in the eCRF. The investigator is to instruct the subject to notify the study site about any new medications he/she takes after the start of the test article. All medications and significant non-drug therapies (including physical therapy and blood transfusions) administered after the subject starts treatment with test article must be listed in the

eCRF. In addition, for antibacterial agents and anti-emetics administered, the dose, unit, frequency and route must be entered in the eCRF.

If a medication is taken prior to the first dose of test article or if their start date is unknown, it will be summarized as a prior medication. Medications are considered concomitant if taken on or after the first dose of test article, or if their stop date is unknown or marked as continuing. Thus, in cases where a medication starts prior to the first dose, and continues throughout the treatment period, the medication will be summarized as both prior and concomitant.

Summary of prior antiemetic and antibiotic medications will also be provided for ITT and micro-ITT populations.

6.6 Protocol Deviations

Deviations will be reviewed in a blinded manner by the sponsor and categorized into general categories (eg. inclusion/exclusion criteria). The sponsor will also categorize the protocol deviations as major and minor. Review of deviations will be conducted and finalized prior to unblinding the database. A major deviation is defined as one that potentially affects the efficacy and/or safety analyses.

The number and percentage of subjects with at least one major protocol deviation or at least one minor protocol deviation will be summarized for the ITT, micro-ITT, and CE-PTE populations. The summaries of major deviations will also be presented by category.

6.7 Other Baseline Summaries

Abnormal laboratory results and abnormal vital signs at baseline will be reported. For further details refer to [Section 8.5](#).

At Screening a full physical examination will include the examination of general appearance, skin, neck (including thyroid), eyes, ears, nose, throat, lungs, heart, abdomen, back, lymph nodes, extremities, and vascular and neurological systems. Only changes from Screening assessments will be recorded as AEs in the eCRFs. If indicated based on medical history and/or symptoms, rectal, external genitalia, breast, and/or pelvic exams may be performed. Subject listings of all physical examination results by body system will be provided. Any changes from baseline will be recorded as AEs.

7 EFFICACY ENDPOINTS AND ANALYSES

7.1 Efficacy Endpoints

The efficacy endpoints are as follows:

	Endpoint	Visit	Population
Primary	Overall Investigator's assessment of clinical response	PTE	ITT
Secondary	Investigator's assessment of clinical response	EOT	ITT CE-EOT micro-ITT
	Overall Investigator's assessment of clinical response	PTE	CE-PTE micro-ITT
	Overall (Sustained) Investigator's assessment of clinical response	FFU	ITT CE-FFU micro-ITT
	Microbiologic response	EOT	micro-ITT ME-EOT
	Overall Microbiologic response	PTE	micro-ITT ME-PTE
Exploratory	UTISA	by timepoint	ITT, micro-ITT, CE-EOT, CE-PTE, CE-FFU
Sensitivity			

Note: Microbiological response is summarized both by patient and by pathogen

7.1.1 Investigator's assessment of clinical response

The primary efficacy endpoint is the investigator's assessment of clinical success at the PTE visit in the ITT population. Detailed definition is included in [Section 7.1.1.2](#).

Additional efficacy endpoints are described below.

7.1.1.1 EOT Visit Clinical Response Assessment

At the EOT visit (on the day of or within 2 days following the last dose of test article) the investigator will determine whether the subject meets the criteria of 1 of the following clinical outcomes:

- **Clinical Success:** Sufficient resolution of signs and symptoms at the EOT visit such that no additional systemic antimicrobial therapy is required for the current infection.
- **Clinical Failure:** No apparent response to therapy or persistence of signs and symptoms of infection at the EOT visit such that use of additional systemic antimicrobial therapy for the current infection is required.
- **Indeterminate:** EOT visit not completed, due to the subject being lost to follow-up or the subject withdrawing consent, or other specified reason.

7.1.1.2 PTE Visit Clinical Response Assessment

At the PTE visit (Day 14 (\pm 2) days after the subject's first dose of test article), the investigator will determine whether or not the subject meets the criteria of 1 of the following clinical outcomes:

- **Clinical Success:** Sufficient resolution of signs and symptoms at the PTE such that no additional systemic antimicrobial therapy is required for the current infection.
- **Clinical Failure:** No apparent response to therapy or persistence of signs and symptoms of infection or reappearance of signs and symptoms at or before the PTE visit such that use of additional systemic antimicrobial therapy for the current infection is required.
- **Indeterminate:** PTE visit not completed.

For the purpose of analysis, Overall Clinical Response at PTE is determined as follows ([Table 5](#)) from the investigator's assessments at the EOT and PTE Visits as per the CRF:

Table 5 Overall Investigator's Assessment of Clinical Response at PTE Visit

EOT Visit	PTE Visit	Overall Clinical Response at PTE Visit
Success	Success	Success
Success	Failure	Failure
Success	Indeterminate	Indeterminate
Failure	Success	Failure
Failure	Failure	Failure
Failure	Indeterminate	Failure
Indeterminate	Success	Indeterminate
Indeterminate	Failure	Failure
Indeterminate	Indeterminate	Indeterminate

EOT = end of treatment; PTE = post-therapy evaluation.

The Overall Clinical Response is derived based on the “worst case scenario” to accommodate for missing visit assessment and intercurrent events (eg rescue medication at EOT visit). For the ITT and micro-ITT populations, the proportion of subjects with a Clinical Success is defined using the following formula (missing information at the PTE visit will be counted as Indeterminate):

$$\frac{\text{\# of subjects with Clinical Success}}{\text{\# of subjects with Clinical Success} + \text{\# of subjects with Clinical Failure} + \text{\# of subjects with Indeterminate response}}$$

By definition, subjects in the CE-PTE population cannot have an Indeterminate response. Thus, for the CE population, the proportion of subjects with a Clinical Success is defined using the following formula:

$$\frac{\text{\# of subjects with Clinical Success}}{\text{\# of subjects with Clinical Success} + \text{\# of subjects with Clinical Failure}}$$

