7.14 Permitted Treatments

All other treatments not specified as prohibited are permitted during the study. Subjects requiring additional or alternative antibacterial therapy for their cystitis will be judged as Clinical Failures and test article will be discontinued. Further treatment for their infection is

at the discretion of the investigator or the subject's health care provider and will be considered as a concomitant medication.

Subjects should be encouraged to contact site personnel before starting any new treatment.

For all treatments received by the subject during the study, relevant information must be recorded on the subject's eCRF.

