8.7.1.2 Investigator's Assessment of Clinical Response at PTE

The investigator will determine whether or not the subject meets the criteria of 1 of the following clinical outcomes:

- **Clinical Success:** Sufficient resolution of signs and symptoms at the PTE such that no additional systemic antimicrobial therapy is required for the current infection.
- **Clinical Failure:** No apparent response to therapy or persistence of signs and symptoms of infection or reappearance of signs and symptoms at or before the PTE visit such that use of additional systemic antimicrobial therapy for the current infection is required.
- **Indeterminate:** PTE visit not completed.

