12.5 Primary Endpoint(s)

12.5.1 Efficacy Endpoint

The primary efficacy endpoint is the Investigator's assessment of clinical success at PTE in the ITT population. The number and percentage of subjects with an Investigator's assessment of clinical success, clinical failure and indeterminate response at the PTE visit will be determined by treatment group in the ITT population. Exact 95% confidence intervals will be determined for the point estimates of the clinical success rates in each treatment group.

A comparison of the clinical success rate at the PTE Visit between each omadacycline dose group and the nitrofurantoin group will be conducted using a beta distribution with an uninformative Bayesian prior distribution. Additional analyses on the primary efficacy endpoint will be performed using Bayesian modeling. Details are described in SAP.

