4.4 Clinically Evaluable Population

The clinically evaluable (CE) population will consist of all ITT subjects who received test article, have a qualifying infection, an assessment of outcome, and meet all other evaluability criteria as described below.

Inclusion into the CE populations will be determined programmatically based on the data on the electronic case report form (eCRF) and a manual review by the Sponsor as necessary prior to unblinding. Details on allocation to each CE population are described in the [Pathogen and CE Review Plan: PTK0796-uUTI-17201²](#).

Since patient count may differ depending on timepoint, CE populations will be defined by milestone visit (CE-EOT, CE-PTE and CE-FFU).

To be included in the CE populations, subjects must meet all criteria defined below:

1. Qualifying infection:

- Exclusion Criterion #2, 3, and 4; Note: for subjects randomized after amendment 1 or later exclusions 3 and 4 are not applicable.

2. Assessment of outcome for CE population:

Subjects must meet all of the following to be included in any CE populations:

- Subject did not meet any of the exclusion criteria 1 and 7 through 10 in the protocol (Baseline event exclusion).
- Received the randomized test article and was at least 80% compliant with the dosing regimen (Compliance to test article intake).
- Study personnel involved in the assessment of efficacy remained blinded to study treatment, unless a treatment limiting AE occurred that required emergency unblinding.

In addition, for each endpoint the following needs to be satisfied, as appropriate:

a. For the CE-EOT population:

- i. Completed the investigator's assessment of clinical response (ie, was not deemed an indeterminate outcome) at the EOT visit

- ii. The EOT visit occurred on the day of, or within +2 days following the last dose of test article (3-day window).
- b. For the CE-PTE population:
 - i. The Overall Clinical Response (based on the investigator's assessment) at the PTE Visit is not Indeterminate (see [Table 5](#))
 - ii. The PTE Visit occurred on Day 14 (\pm 2 days) after the subject's first dose of test article, unless the subject was considered to be a Clinical Failure based on the investigator's assessment at the EOT visit.
- c. For the CE-FFU population:
 - i. The Overall (Sustained) Clinical Response (based on the investigator's assessment) at the FFU Visit is not Indeterminate (see [Table 6](#))

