Per-pathogen and per-subject overall microbiological responses at PTE are determined as follows (Table 9) from the per-pathogen and per-subject microbiological responses at the EOT and PTE Visits:

Table 9 Microbiologic Response at PTE

Microbiologic Response at EOT Visit	Microbiologic Response at PTE Visit	Overall Microbiologic Response at PTE
Favorable	Favorable	Favorable
Favorable	Unfavorable	Unfavorable
Favorable	Indeterminate	Indeterminate
Unfavorable	Favorable	Unfavorable
Unfavorable	Unfavorable	Unfavorable
Unfavorable	Indeterminate	Unfavorable
Indeterminate	Favorable	Indeterminate
Indeterminate	Unfavorable	Unfavorable
Indeterminate	Indeterminate	Indeterminate

Favorable is defined as the eradication of the baseline pathogen.
 Unfavorable is defined as the persistence of a baseline pathogen
 EOT = end of treatment; PTE = post-therapy evaluation.

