9 CHANGES FROM PROTOCOL

Not applicable.

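### SAP Table 5 scores an observed PTE success as a non-success when only the EOT visit was missed, an undeclared departure from the protocol's primary endpoint

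*SAP*

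**What the plan says.** Protocol 12.5.1 makes the primary endpoint the investigator's "assessment of clinical success at PTE in the ITT population". Protocol 8.7.1.2 gives Indeterminate at PTE a single trigger: "PTE visit not completed". Its Clinical Failure category covers "reappearance of signs and symptoms at or before the PTE visit" where further systemic antimicrobial therapy is required.

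SAP 7.1.1.2 repeats these visit-level definitions. It then derives an Overall Clinical Response from the EOT and PTE ratings (Table 5), described as a worst-case derivation "to accommodate for missing visit assessment and intercurrent events (eg rescue medication at EOT visit". In Table 5, EOT Indeterminate with PTE Success gives Indeterminate. The success formula for ITT and micro-ITT keeps Indeterminate in the denominator, and SAP 7.2 bases the primary outcome on overall clinical success. SAP 4.4 admits a subject to CE-PTE only if her Overall Clinical Response "at the PTE Visit is not Indeterminate".

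SAP Section 9, on changes from the protocol, reads "Not applicable". SAP Section 1 says that the SAP prevails where the two differ and that the Clinical Study Report will explain the differences.

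**The concern.** A woman seen at PTE and rated a success has the outcome that the protocol names as primary. Table 5 sets it aside because an earlier visit was not done. She becomes a non-success in the primary analysis and disappears from CE-PTE. Table 6 then keeps her Indeterminate at final follow-up even if she is a success there too.

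The SAP's example for the rule is rescue medication. The protocol already deals with that: "Subjects requiring additional or alternative antibacterial therapy for their cystitis will be judged as Clinical Failures" (Section 7.14), and Section 7.12 requires antibacterials to be entered in the eCRF with dose, unit, frequency and route. The record therefore offers a more direct way to detect rescue than assuming the worst of everyone who missed EOT.

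The primary comparison is a difference against a 10-point margin, so an imbalance in missed EOT visits would move it without any difference in efficacy. An arm-related route is possible. EOT procedures are due on the day a subject stops dosing (Protocol 9.4), some dosing days are spent at home (9.3), and early discontinuers complete later visits only if possible (8.17). The documents do not show that such an imbalance exists.

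**Working it through.** **Side by side**

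| EOT rating | PTE rating | Protocol 8.7.1.2 | SAP Table 5 | Counted in ITT under SAP |
|---|---|---|---|---|
| Indeterminate | Success | Success | Indeterminate | Non-success |
| Indeterminate | Failure | Failure | Failure | Non-success |
| Success | Indeterminate | Indeterminate | Indeterminate | Non-success |

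Of these three rows, only the first differs. SAP 5.1.3 uses EOT data in ITT and micro-ITT whenever the visit took place, so a late EOT does not trigger the rule. Only an EOT not done does.

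**Inputs.** From SAP 3.1: true success rate 0.82 in both arms, posterior target 0.80, about 225 subjects. From SAP 3.2: 1:1:1:1:1 allocation, so 225/5 = 45 per arm if the ratio is unchanged. From SAP 7.2: margin 0.10, Beta(0.5, 0.5) priors, posterior P(pOMC − pN > −0.10 | data). Assumed, because no document gives it: m, the share of PTE successes whose EOT visit was not done.

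**The plan's own figure.** SAP 3.1 states about 79% at 50 per arm and 80% at 53. Exact enumeration of both binomials with these inputs gives 69.2% and 69.5%. The stated figures are not reproduced. That is a separate matter, and the comparisons below all use the enumeration, so they do not depend on it.

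**Rate under Table 5.** Reported rate = 0.82 × (1 − m). For m = 2%: 0.82 × 0.98 = 0.804. For 5%: 0.82 × 0.95 = 0.779. For 8%: 0.82 × 0.92 = 0.754. For 3%: 0.82 × 0.97 = 0.795. The shift in the difference (omadacycline minus nitrofurantoin) is 0.82 × (mN − mOMC).

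**Chance that the posterior reaches 0.80, 45 per arm, true rates equal at 0.82**

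| m omadacycline | m nitrofurantoin | Shift in difference (points) | Chance of reaching target |
|---|---|---|---|
| 0 | 0 | 0 | 66.7% |
| 2% | 2% | 0 | 65.7% |
| 5% | 5% | 0 | 64.4% |
| 2% | 1% | −0.8 | 62.3% |
| 5% | 2% | −2.5 | 54.0% |
| 8% | 3% | −4.1 | 45.9% |
| 3% | 8% | +4.1 | 79.7% |

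**In subjects.** At 45 per arm, 37 v 37 successes gives a posterior of 0.895, 36 v 37 gives 0.832 and 35 v 37 gives 0.753. Two reclassified omadacycline successes are enough to fall below the target.

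**Equal missingness is not always conservative.** With true rates 0.72 v 0.82 and m = 10% in both arms, the reported difference is 0.648 − 0.738 = −0.09 instead of −0.10. At 50 per arm the chance of reaching the target rises from 20.8% to 25.3%.

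**The case against.** The rule is stated openly in SAP 5.1.2 and 7.1.1.2, is fixed before unblinding and is the same for every arm. The SAP says that it prevails. That stands: this is a prespecified composite, and the fault lies in the choice of rule and in Section 9's silence.

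A reader might infer that a PTE Success already carries everything known up to that visit, so that nothing is missing. The documents do not support this. Table 5 scores EOT Failure with PTE Success as Failure, precisely because a subject rescued earlier could look resolved at PTE. With EOT unseen, a rescued subject and a cured one can share the same PTE rating. Any replacement rule therefore has to check for rescue.

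A reader might also extend the point to Table 9, where "Per-pathogen and per-subject overall microbiological responses at PTE are determined as follows" and EOT Indeterminate with PTE Favorable gives Indeterminate. That does not hold. The protocol names an indeterminate microbiologic response (12.6.2) but never defines one at PTE, so Table 9 contradicts no protocol definition. SAP 5.1.2 also provides an imputation for missing EOT microbiology.

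On size, subjects who miss both visits are Indeterminate under either rule, and late EOT visits still count. The blinded review of the first 145 subjects (Protocol 7.4) found one discontinuation for nausea or vomiting, although it predates the twice-daily 450 mg arm. The 8% v 3% case is therefore illustrative and has no support in the documents. An imbalance would also be visible: SAP 6.1 tabulates visit completion and reasons for missed visits, and 7.3.1 tabulates reasons for Indeterminate.

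Finally, the content of SAP 7.5 is redacted. It cannot be said that no sensitivity analysis covers this.

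**Conclusion.** The concern holds for the clinical endpoint. Table 5 turns an observed PTE success into a non-success in ITT and micro-ITT, and removes the subject from CE-PTE, when only EOT was not done. This departs from Protocol 8.7.1.2 and 12.5.1, and SAP Section 9 does not declare it.

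Relative to the protocol endpoint, the effect is downward on each arm's rate. On the between-arm difference it can go either way, so the documents do not support reading the rule as biased against omadacycline, or as reliably conservative. Its size depends wholly on the assumed missed-EOT rate among PTE successes. Small rates (2% in both arms, or 2% v 1%) cost about 1 to 4 percentage points in the chance of reaching the target. An imbalance of 5 points moves it to 45.9% or 79.7%, from 66.7%. These figures assume 45 per arm, true rates of 0.82 and an unchanged allocation ratio. The point is worth correcting because two subjects can decide whether the target is reached. It does not show that the result will be wrong.

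**What to change.** In SAP Table 5, score EOT Indeterminate with PTE Success as Success for the ITT and micro-ITT analyses, unless the concomitant-medication record shows a non-study systemic antibacterial for the current infection before PTE. Leave the EOT Failure rows as they are. Keep the present Table 5 as a worst-case sensitivity analysis.

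If the sponsor prefers the composite as primary, declare it in SAP Section 9 as a change from the protocol and report the PTE-only result, under the protocol's definition, beside it.

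In either case, first check whether the redacted Section 7.5 already contains such an analysis. The cost is a wording change, one more derivation to program and one more table. No additional data collection is needed.
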